6.0 Protection of Human Subjects

Human Subjects Involvement and Characteristics. The purpose of this study is to assess the acceptability, feasibility, and usability of an intervention designed to reduce anxiety sensitivity and functional impairment among Veterans with elevated anxiety sensitivity experiencing functional impairment. A total of 15 participants will be recruited through the Canandaigua VA and receive Brief Enhanced Anxiety Sensitivity Treatment (BEAST) through telehealth and supplemented via a mobile app.

Source of Materials. Study materials will include self-report questionnaires. The materials will be collected for study purposes only. Information collected will be stored in a locked filing cabinet in a locked office at the study sites that can only be accessed by members of the study team. *All electronic data* will be stored on VINCI project servers. Only approved study team personnel who will be involved in data entry, management and analyses will be granted access to this data. All computers are password protected.

Recruitment and Informed Consent.

All research staff conducting recruitment and informed consent will have completed appropriate and up-to-date training in research, research ethics and the proper conduct of research that includes common issues related to recruitment and informed consent.

Veterans will be identified using structured queries of VA administrative datasets. Research staff will use these lists to identify potentially eligible participants and to enhance the number of Veterans at high risk, women and/or minorities recruited into the study. Research staff will mail an IRB-approved letter describing the study to the Veteran. Research staff will call all patients who receive a letter unless the patients call a number to opt out. These are Syracuse VA IRB-approved procedures that are used by researchers at the Center of Excellence for Suicide Prevention and Syracuse VAMC. There is no more than minimal risk to the participants and the rights of the participants, or their welfare, will not be adversely affected. Recruitment and informed consent procedures were designed to ensure patients do not feel like participation is required. Patients unable to understand the informed consent process will be excluded from participating. Screening interviews will be completed initially over the telephone (using a script)

to assess eligibility criteria. Verbal consent will be obtained at this time to complete the screening. Participants screening positive for exclusion criteria will not be included in the study. Veterans who report suicidal intent with a plan will be transferred to the Veteran's Crisis Line (as detailed below in Protection Against Risk). For eligible and interested participants, a research assistant will review the consent form and complete a brief questionnaire to ensure the potential participant understands the study.

Participants will receive compensation for their participation in the study due to the time commitment required. The compensation amount will be based on the schedule that follows per aim, also found earlier in this protocol:

Aim 1:

Prior to Pilot Study	\$50
Completion of Pilot Study	\$50

Stakeholders will be provided compensation prior to the pilot study when feedback is given, as well as after the pilot study has been completed for a total of \$100 as compensation for their time.

Aim 2:

Baseline Assessment	\$40
Post-Intervention Assessment	\$40
1-month Assessment	\$30
3-month Assessment	\$30
Weekly EMA Data Collection	\$30 per week
≥ 80% of EMA Weekly Surveys	\$10 per week

Therefore, the total compensation for completing all the Aim 2 study components would be \$340. Payments will be made following each study procedure listed above. Participants who do not complete the entire study for any reason, will receive compensation for the components that were completed per the above schedule of payments.

Protection Against Risk.

Anticipated risks to the participants from assessment procedures and therapy are minimal; however, participants may experience psychological distress, frustration, and/or fatigue. The semi-structured interviews, assessments associated with the intervention, and therapy sessions encourage participants to recall personal events and life stressors that may evoke distress. Participants will be told they can withdraw from the study at any time. Participation or withdrawal from the study will not affect any benefits to which they are otherwise entitled. Special precaution will be taken to safeguard confidentiality.

All assessors and interventionists will have a specific protocol to follow regarding emergency care and will have the clinical back-up of Drs. [name], [name], and [name]. This study will use safety procedures that have been previously approved by the IRB in several of our protocols. All research staff will be thoroughly trained on these procedures. These include written procedures for handling emergencies, a written procedure for conducting a full suicide risk assessment whenever suicidality is endorsed, procedures for participants endorsing a suicidal plan or intent (including staying with a patient until they are connected with a mental health provider or 911

help), and a written warm-handoff guideline to connect Veterans to the National Veterans/Military Crisis Line (VCL).

In any of the above instances, the research staff member will read (or paraphrase) the following statement to the participant at the end of the call:

I am concerned about your safety and so at this time I am going to transfer you to speak with one of our mental health clinicians at the Veterans/Military Crisis Line. There will be a moment of silence as I connect you. If for some reason we get disconnected please dial [name] and press #1 to reach the Lifeline. I will stay on the line with you until the transfer is complete. I am now going to transfer you. Please stay on the line.

The researcher will briefly summarize the participant's situation to orient the VCL responder to the nature of the call (the participant will hear a moment of silence at this time, and then the participant will be transferred to the VCL).

If the participant hangs up or becomes disconnected, the researcher will call the VCL immediately, and the VCL staff will take necessary actions as appropriate according to the VCL safety protocol and/or direct the researcher what actions to take. These actions may include initiating a "rescue" that involves calling 911 at the participant's local jurisdiction and having emergency personnel come to the participant's home to ensure their safety. The VCL staff performs rescues every day, and all rescues are done in collaboration with a supervisor. We have ongoing collaborations with the VCL and have substantial experience working with responders and supervisors. Our approach to participant safety will be applied to all participants including control participants and is guided by ongoing clinical and research experience in suicide prevention, including our Center Director's affiliation with the VCL.

We will collaborate closely with the VCL during the study start-up phase to review these safety protocol steps. As a reminder, the VCL, which was established in 2007 at the Canandaigua VAMC, can be reached anytime by calling [name]. The VCL has grown to be one of the largest in the world, with a full-time staff of more than 600 full-time responders. VCL responders are paid professional staff and nearly all have a Master's degree in a relevant field (e.g., mental health counseling), distinguishing the VCL from others in the U.S. that are staffed primarily with volunteers.

VCL resources will be available as back-up at all times during study sessions. VCL responders are arguably the foremost experts in managing acute suicidal crises via telephone. They have in place protocols for locating suicidal individuals, identifying the closest police and emergency medical services, and monitoring and documenting "rescues." Moreover, VCL responders have the ability to look up call histories based on callers' phone numbers, a capability that since implemented has greatly aided the ability of responders to rapidly assess callers' needs.

All participants will be provided the VCL phone number at the end of each baseline assessment and at each follow-up assessment and encouraged to call the number should they become suicidal, simply wish to talk with someone, or would like assistance in obtaining a referral for mental health treatment. In situations in which potential suicide risk is identified during a phone call, we plan to use two levels of response: 1) researcher transfers the individual to the VCL (used in acute crises requiring emergency intervention or "rescue"); 2) researcher offers the participant a transfer to the VCL, but does not perform the transfer if he/she does not wish to be transferred (used in non-emergency situations).

Breach of Confidentiality. Statistical data files will be kept on VINCI project servers maintained by VINCI OI&T personnel and only summarized data without protected health information (PHI) will be downloaded from VINCI to local storage media. Research staff will use an audited VINCI download utility to move summarized data for reports, presentations and publications from VINCI servers to local storage media. The VINCI download utility provides an audit path including a copy of the downloaded material. The data extraction tool will be adapted for use with software directly available on the VINCI platform (e.g. Microsoft Word and Excel) and study data will be stored and maintained on VINCI. All study team personnel with access to sensitive patient data will stay current on their VA approved information security training and VA approved privacy policy training.

Adverse Events (AE). All research staff will participate in an intensive training to help them understand the importance of reducing the risk for participants and learning how to recognize and report any AE or SAE. AEs may include, but are not limited to: worsened physical or mental health, or inadvertent disclosure of confidential research information. Serious Adverse Events (SAE) may include: death, hospitalization due to worsening psychiatric symptoms or suicidal ideation, or all life threatening or disabling/incapacitating events among research participants. Per IRB regulations, SAEs, any event resulting in a deviation from the study protocol (e.g., emergency hospitalization to address suicidal behaviors) or death will be reported to the PI within 24 hours and to the IRB in 48 hours. He will make a decision whether there is sufficient evidence to suspend data collection, allow for further IRB review, modify the protocol, or make other changes to reduce potential risk to participants. The study will resume based on agreement of the PI, and an IRB member (the chair will recuse himself because he is a co-I on the study). Immediate evaluation will occur to determine if any extra steps can be taken to minimize the likelihood of that type of AE occurring again. If changes can be made, a report/amendment will be written and submitted to the IRB. AEs that involve temporary distress will be noted by interviewers and provided to the IRB in an annual report.

Confidentiality of Records: Numerous protections are in place to reduce the likelihood of loss of confidentiality. All research data will be kept in locked filing cabinets in secure areas, absent of identifying information, and coded by research number only. Files containing consent forms and other items with identifying information will also be kept in locked filing cabinets, but these will be separate from cabinets containing data from this study. Social security numbers (SSNs) may be collected based on the participant's preferred payment methods. These SSNs would only be used as part of fiscal forms needed for payment, and these payment vouchers would be stored within protected electronic folders for documentation purposes only.

Potential Benefits of Research to Participants and Others. There may be direct and/or indirect benefits of study participation. Participants may benefit from receiving the intervention as it is designed to reduce sensitivity to anxiety. Participation in this intervention will benefit future Veterans as we can identify if these interventions can reduce anxiety and improve functional impairment in Veterans experiencing elevated anxiety sensitivity. Dissemination of the findings from the study will contribute to the extant literature and will inform future implementation efforts.

Importance of Knowledge to be Gained. This study is important to science and society because there is an urgent need for brief interventions to help individuals that experience anxiety and anxiety sensitivity. This study represents an important step towards making these interventions more accessible. Ultimately, this intervention could be an efficient means to reduce anxiety in Veterans.

Data Safety & Monitoring Plan

Data Safety. To ensure safety of participants in the study proposed and validity and integrity of data collected, the PI ([name]) will oversee all data and safety monitoring functions and the research team will be advised that he will be the primary contact overseeing these activities. The investigators will meet regularly to monitor study progress and discuss the implementation of monitoring procedures. The PI will also meet regularly with the research coordinator and staff to review monitoring procedures and ensure all efforts are being taken to minimize risks to participants. As indicated above, the PI will track all negative outcomes and incidents as well as conduct interim data analysis every 12 months after the study has started. The study design will be significantly modified if the study is creating potential harm to our participants.

The PI and [name] will regularly oversee all aspects of the study, including participant recruitment, informed consent, data collection, management, and analysis, as well as regularly assess the risk/benefit ratio associated with participation in the study.

As part of a standard practice, the PI will supervise the implementation of one audit within 4 months after study recruitment and one regularly per year afterwards of the materials collected and produced as part of the study at each site to ensure proper confidentiality and compliance with ethical principles, including informed consents, questionnaire data, and to make sure that the research staff are following established protocols. The PI will provide an annual summary report of all AEs to the IRB as part of the annual review. If no adverse events have occurred, the report will state, "No adverse events affecting human participants have occurred during this project year."

Data Monitoring. To ensure adequate participant recruitment and enrollment, each week, the PI will discuss the current number of participants contacted, screened, and enrolled from each site and compare those numbers to the expected based on our preliminary data. If after the first 4 months, it appears we are not reaching our expected number of participants, the PI will discuss potential barriers/obstacles and solutions with the research team and we will enact contingency plans as needed.

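### Section 6.0 gives conflicting instructions for a Veteran who endorses suicidality without an emergency, and its thresholds for the stronger response do not match

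*Combined protocol and SAP*

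**What the plan says.** All the relevant text is in section 6.0 of the combined protocol and SAP.

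- **Recruitment and Informed Consent.** At screening, a Veteran who reports suicidal intent and also has a plan is transferred to the Veterans Crisis Line (VCL). The sentence sends the reader to Protection Against Risk for the detail.
- **Protection Against Risk, list of procedures.** The list covers emergencies, "a written procedure for conducting a full suicide risk assessment whenever suicidality is endorsed", "procedures for participants endorsing a suicidal plan or intent" (staff remain with the Veteran until a mental health provider or emergency help has taken over), and a warm-handoff guideline to the VCL.
- **Protection Against Risk, script.** The next sentence reads "In any of the above instances, the research staff member will read (or paraphrase) the following statement to the participant". The script tells the Veteran that a transfer is about to happen and closes with "I am now going to transfer you. Please stay on the line". It contains no question and no option to refuse.
- **Protection Against Risk, two-level rule.** Further on: "In situations in which potential suicide risk is identified during a phone call, we plan to use two levels of response". Level 1 is a transfer, "used in acute crises requiring emergency intervention". At level 2, for non-emergency situations, the "researcher offers the participant a transfer to the VCL, but does not perform the transfer if he/she does not wish to be transferred".

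**The concern.** The list names any endorsement of suicidality separately from plan or intent, and the script is then attached to every instance above it. Read as written, a Veteran who reports passing suicidal thoughts, with no plan, no intent and no emergency, is told that a transfer is being made. The two-level rule says that the same Veteran should be asked and may say no. Neither text limits or refers to the other.

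The situation is foreseeable. Section 5.5 includes a four-item suicidality measure among the assessments completed via research staff. The only suicide-related exclusion that section 5.4 names is an imminent suicide crisis, so suicidality short of that is not a listed bar to enrolment.

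At stake is whether staff respond in the same way to the same disclosure. They could impose a transfer on someone entitled to decline it. They could also be unsure how firmly to act for a Veteran who has intent without a plan, or a plan without intent.

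**Working it through.** No arithmetic applies. The check is to take defined cases on a phone call and read off what each text in section 6.0 requires.

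| Case | Screening sentence (Recruitment and Informed Consent) | List and script (Protection Against Risk, as worded) | Two-level rule (Protection Against Risk) |
|---|---|---|---|
| A. Suicidal thoughts, no plan, no intent, no emergency | Threshold not met | Full risk assessment, then transfer announced with no option to decline | Transfer offered; refusal accepted |
| B. Intent, no plan | Threshold not met | Stay until connected; transfer announced | Level 1 or level 2, depending on whether staff judge it an acute crisis |
| C. Plan, no intent | Threshold not met | Stay until connected; transfer announced | Level 1 or level 2, as in B |
| D. Intent and plan | Transfer | Stay until connected; transfer announced | Presumably level 1, though the rule does not say so |

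Step 1: case A. The list-and-script text and the two-level rule both apply, and they give opposite answers on whether a refusal is accepted. The conflict depends on the script's scope including the item on any endorsement. That is the plain reading: the item stands in the list directly above and describes an occasion on which staff act.

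Step 2: the narrower reading. Suppose the script is meant only for level 1. The conflict in case A then disappears, because the Veteran is assessed and offered a transfer.

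Step 3: cases B and C on the narrower reading. Three thresholds remain: intent with a plan, plan or intent, and acute crisis. The third is not defined and is not tied to either of the others. Intent without a plan falls below the first, meets the second, and is left to judgement under the third. The mismatch therefore survives the charitable reading.

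Step 4: case D. All three texts point the same way, or nearly so. The most severe presentation is not where the difficulty lies.

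**The case against.** The strongest reply is that the conflict needs an unlikely reading of the script. What stands above the script is a list of procedures, so its reference to instances is loose. If every endorsement led to a transfer, the full risk assessment would decide nothing. The script follows the warm-handoff guideline directly, may be paraphrased, and reads naturally as the wording for a transfer already decided on. The screening threshold also suggests that transfers were meant for severe cases. Staff are trained on written procedures that the protocol does not reproduce, they have clinical back-up, and the steps are to be reviewed with the VCL at start-up. Most of this stands as evidence of intent. It does not change the text, and the screening sentence presents this subsection as the place where the detail is given.

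A reader might infer four stronger things, none of which the documents support.

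- **That declining an offer sets off a call to the VCL and possibly a rescue.** The sentence "If the participant hangs up or becomes disconnected, the researcher will call the VCL immediately" follows the transfer steps. Declining a level 2 offer is neither of those events, and no text links the two.
- **That a Veteran with a plan or intent may simply be offered a transfer and left.** The list requires staff to stay until that Veteran is connected. An under-response of that kind would mean ignoring an explicit instruction.
- **That video contacts are unprotected.** The two-level rule names phone calls only, but the subsection's emergency protocol covers all assessors and interventionists, and VCL back-up is available throughout study sessions.
- **That the conflict will arise in some stated number of contacts.** The documents give no endorsement rate and do not say at which assessments the suicidality measure is given.

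**Conclusion.** The point holds as an internal inconsistency in a safety instruction. For one non-emergency endorsement by phone, the text as worded gives two responses that differ on whether a refusal is accepted. Across section 6.0 there are three thresholds that do not match, and they separate in practice for a Veteran with intent but no plan, or a plan but no intent.

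The first part rests on reading the script's scope as written; if it was meant for level 1 only, which is probable, that part is a drafting slip. The second part does not depend on that reading. Both could be settled by the separate written procedures, which the protocol does not reproduce. This is a minor correction, worth making because it concerns participant safety. It has no bearing on the sample size, the feasibility benchmarks or the analysis.

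**What to change.** In section 6.0:

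1. Under Protection Against Risk, limit the transfer script to the level 1 response, and add a short second wording for level 2 that offers a transfer and accepts a refusal.
2. Define level 1 by one threshold. Plan or intent would match the existing list; the sponsor may choose another. Use that threshold in the screening sentence, in the list above the script and in the two-level rule.
3. Optionally, extend the two-level rule from phone calls to any study contact, so that video assessments and the intervention session are expressly included.

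If the separate written procedures already contain such a rule, copy it into these places. The cost is an amendment to about three sentences and one added script, with no new visit, measure or data field.
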